5.4.2 STUDY VISITS

Table 2 shows the summary of the 3 study visits.

Table 2: Summary of visits

Visit code	Visits
1	Screening (1.5 hours)
2	Review habitual DD lenses and dispense DT1, 6-14 days after V1 (1.0 hour)
3	Review DT1 and study exit, 29-34 days after V2 (1.0 hour)

Visit 1 (Day 0 for habitual DD): Screening (1.5 hours)

- Informed consent procedure

- Participants will attend this visit wearing their habitual spectacles. They will be asked to stop lens wear for \geq 12 hours prior to the visit and will be asked to bring a new pair of their habitual lenses with them.
- The purpose of this visit is to determine participant eligibility and to classify the type of DED exhibited by the participant, using TFOS DEWS II guidelines. These tests will include:
 - OSDI questionnaire (with participant reflecting on their ocular symptoms without CL wear);
 - Tear osmolarity (TearLab);
 - Non-invasive tear break-up time (using the Oculus K5M);
 - Tear meniscus height assessment (using the Oculus K5M);
 - Meibomian gland assessment (to calculate a meibomian gland score) using the meibomian gland evaluator (Johnson & Johnson Vision);
 - Ocular surface staining assessment and lid wiper staining;

To minimize disruption of the ocular surface, these tests will be conducted in the order of the least invasive, through to the most invasive.

- Participants will complete a CLDEQ-8 questionnaire to review their experience with their habitual lenses over the past two weeks.
- A full slit lamp biomicroscopy examination will also be performed to determine ocular health, including ocular hyperemia and surface staining with fluorescein.
- Participants will undergo a subjective refraction (Distance High Contrast High Illumination [HIHC] visual acuity, OD, OS & OU) and will be fit with DT1 to confirm acceptable visual acuity and lens fit.
- Participants will be asked to insert their habitual lenses to confirm acceptable visual acuity and lens fit.
 - Distance HCHI visual acuity with habitual lenses, OD, OS & OU
- If the participant meets all inclusion / exclusion criteria, the participant will be instructed to wear their habitual DD CLs as usual until their next scheduled visit.
- Participants will be provided with a subjective rating questionnaire (related to comfort, dryness, handling, onset time of discomfort, total wear times and reasons for lens removal) to be completed at home on Days 1, 3 and 5. Participants will be instructed that they must wear the lenses on the days where they are required to complete the ratings, and will be scheduled to return for their next visit between 6 and 14 days after the screening visit.

Visit 2 (Day 0 for DT1): Review habitual DD lenses and dispense DT1, 6-14 days after V1 (1.0 hour)

- Participants will attend this visit wearing their habitual DD CLs for \geq 2 hours prior to the visit.
- The subjective ratings completed at home will be reviewed.
- In-office subjective ratings of a typical day for comfort, dryness, vision and handling (with CLs; 0 to 100 scale), plus total wear time and comfortable wear time (onset time of discomfort) per day over the last month.

- The following assessment of the habitual lenses will be made:
 - Distance HCHI visual acuity, OD, OS & OU;
 - Lens surface characteristics: wettability and deposition;
 - Lens fit.
- After lens removal, a slit lamp biomicroscopy examination (including assessments for ocular surface staining and hyperemia) will be performed.
- DT1 will be dispensed and the following assessments will be made:
 - Distance HCHI visual acuity, OD, OS & OU;
 - Lens surface characteristics: wettability and deposition;
 - Lens fit.
- Participants will be provided with a 1 month supply of overlabeled DT1 CLs (for masking) and instructed to wear the lenses at least 3 days per week and 6 hours per day throughout the study.
- Participants will be provided with a subjective rating questionnaire (related to comfort, dryness, handling wear times and reasons for lens removal) to complete at home on Days 1, 3, 5, 7, 21, 28. Participants will be instructed that they must wear the study lenses on the days where they are required to complete the ratings, and will be scheduled to return for their next visit between 29 and 34 days after V2.

Visit 3: Review DT1 and study exit, day 29-34 days after V2

- Participants will attend this visit wearing the study CLs for \geq 2 hours prior to the visit.
- Participants will be asked to complete a CLDEQ-8 questionnaire to review their experience with the DT1 study lenses.
- The subjective ratings completed at home will be reviewed.
- In-office subjective ratings of comfort, dryness, vision and handling (with CLs; 0 to 100 scale), total wear time and comfortable wear time (onset time of discomfort) over the last month.
- The following assessment of the study lenses will be made:
 - Distance HCHI visual acuity, OD, OS & OU;
 - Lens surface characteristics: wettability and deposition;
 - Lens fit.
- Slit lamp biomicroscopy examination (including assessments for ocular surface staining and hyperemia).
- Study exit documentation & reimbursement.

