5.5 STUDY PROCEDURES

Table 3 summarizes the procedures at each visit. The order of procedures is described in sections 5.4.2.

Table 3: Summary of procedures to be conducted at scheduled visits

Procedure	Screening Visit 1	Dispense Visit 2	Follow-up Visit 3
Informed consent	X		
Participant demographics (age, sex, ethnicity)	X		
Contact lens history	X		
Medical history and medications	X		
Changes in medical history/ medications		X	X
HCVA (logMAR) (habitual Spectacles)	X		
OSDI questionnaire	X		
CLDEQ-8 questionnaire	X (habitual CL)		X (study CL)
Comfort, dryness, vision, handling ratings, comfortable & total CL wear time over last month	X (habitual CL)		X (study CL)
Non-invasive tear break-up time (Oculus K5M)	X		
Tear meniscus height (Oculus K5M)	X		
Tear osmolarity (TearLab)	X		
Meibomian gland score (MG evaluator)	X		
HCVA (logMAR) (Contact lenses)	X (habitual and study CL)	X (habitual and study CL)	X (study CL)
Biomicroscopy (incl. staining assessment)	X	X	X
Auto refraction/auto keratometry: horizontal and vertical K readings	X		
Subjective refraction	X		
Lens performance (fit, wettability, deposition)	X (habitual CL)	X (habitual and study CL)	X (study CL)
Review of compliance (CL wear, completion of home ratings)		X	X
Subjective at-home ratings provided	X	X	
Study lens fitting	X		
Study lens dispense		X	
Collection of unused study lenses			X
Study Exit			X

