5.5.2 QUESTIONNAIRES AND SUBJECTIVE RATINGS

Questionnaires:

At the screening visit (Visit 1), participants will complete the OSDI questionnaire to reflect their dry eye symptoms.

At visits 1 and 3, participants will complete the CLDEQ-8 questionnaire, reporting their experience with their habitual and study contact lenses, respectively, over the past 2 weeks.

Subjective ratings:

Participants will be provided with subjective rating 0-100 questionnaires related to comfort, dryness, vision, lens handling and will be asked for times of lens insertion and removal and reasons for lens removal as well as onset of discomfort on that day and reason for lens removal. This questionnaire will be completed at home on Days 1, 3, 5 after visit 1 and on Days 1, 3, 5, 7, 21, 28 after visit 2. Participants will be instructed that they must wear the study lenses on the days where they are required to complete the ratings, and will be scheduled to return for their next visit.

The same questionnaire will be provided to the participants during visit 1 and 3 to reflect their overall 'typical day' experience over the previous month.

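### Section 5.4.2 lists the Visit 1 CLDEQ-8 after the dry-eye tests but the Visit 3 CLDEQ-8 before any examination, an avoidable asymmetry of unknown size and uncertain net direction

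*Combined protocol and SAP*

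**What the plan says.** Section 5.5 introduces Table 3 and then sends the reader elsewhere for sequence: "The order of procedures is described in sections 5.4.2".

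In section 5.4.2, the Visit 1 battery runs from the OSDI through tear osmolarity, non-invasive break-up time, tear meniscus height and meibomian gland assessment to "Ocular surface staining assessment and lid wiper staining". A rule on sequence follows: "To minimize disruption of the ocular surface, these tests will be conducted in the order of the least invasive, through to the most invasive". The next bullet is the CLDEQ-8: "Participants will complete a CLDEQ-8 questionnaire to review their experience with their habitual lenses over the past two weeks". Slit lamp examination and refraction come after it.

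At Visit 3, the first task after arrival is: "Participants will be asked to complete a CLDEQ-8 questionnaire to review their experience with the DT1 study lenses". The ratings, visual acuity, lens assessment and slit lamp examination all follow.

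Section 5.5.2 gives the same recall period at both visits, with participants "reporting their experience with their habitual and study contact lenses, respectively, over the past 2 weeks". Lens state differs. At Visit 1, after at least 12 hours without lenses, "Participants will attend this visit wearing their habitual spectacles". At Visit 3 they arrive having worn the study lenses for at least 2 hours.

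Table 4 compares the two CLDEQ-8 scores by a two-sided paired t-test. Inclusion criterion 5 (section 5.2.3) requires a score from 12 to 20. The primary endpoints in section 2 do not include the CLDEQ-8.

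**The concern.** A paired comparison attributes the difference between two scores to the lens only if the scores are otherwise taken alike. As listed, the habitual-lens score follows lid pressure and dye, and the DT1 score follows no examination. Section 7 accepts that study procedures or products may cause temporary discomfort, including burning, grittiness and dryness, and a dryness questionnaire is the kind of instrument that such sensations could colour.

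The study is non-randomized and has no concurrent control, so nothing in the design cancels a measurement condition tied to one visit. Two uses of the score are exposed: the Table 4 CLDEQ-8 comparison and the entry criterion. A raised score could bring in someone whose undisturbed score is below 12, or turn away someone whose undisturbed score is at or just under 20. The rule on sequencing shows that the authors had disturbance of the ocular surface in mind, but it covers the tests and does not mention the questionnaire.

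**Working it through.** **Order, side by side (section 5.4.2)**

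| | Visit 1, habitual lens | Visit 3, DT1 |
|---|---|---|
| Listed before the CLDEQ-8 | OSDI, osmolarity, break-up time, meniscus height, gland assessment, staining | No examination |
| Lens state on arrival | Spectacles, no lenses for at least 12 h | Study lenses in for at least 2 h |
| Recall period (5.5.2) | 2 weeks | 2 weeks |
| Use of the score | Entry criterion and Table 4 | Table 4 |

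The order differs and the recall period does not. A higher score means worse symptoms, since the criterion uses 12 as a minimum. Irritation from the battery, if it entered the answers, would therefore raise the habitual score and make the change to DT1 look better. Lens state is a second difference. Sensation from lenses in the eye at Visit 3 could raise the DT1 score and act the other way.

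**Check of the method on the plan's own figure**

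Section 5.2.1 gives n = 39 for a two-sided paired t-test with α = 0.05, power 0.95 and diff/SD = 0.60. Power is P(|T| > t₀.₉₇₅,ₙ₋₁), where T is noncentral t with n − 1 degrees of freedom and noncentrality d√n.

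- n = 39: noncentrality 0.60 × √39 = 0.60 × 6.245 = 3.747, critical value 2.024, power 0.9546.
- n = 38: power 0.9496, below 0.95.

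The stated 39 is reproduced.

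**Illustration of a pure order effect**

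Inputs from the documents: 39 completers (5.2.2), two-sided 5% paired t-test (Table 4). Assumed, because the documents give neither: a shift b in the Visit 1 score, and an SD of the paired CLDEQ-8 change from 3 to 8 points. The true lens difference is set to zero. Noncentrality = (b/SD) × √39.

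| SD of change | b = 0.5: noncentrality, rejection | b = 1: noncentrality, rejection |
|---|---|---|
| 3 | 1.041, 17.4% | 2.082, 52.8% |
| 4 | 0.781, 11.9% | 1.561, 33.1% |
| 5 | 0.624, 9.3% | 1.249, 23.0% |
| 6 | 0.520, 8.0% | 1.041, 17.4% |
| 8 | 0.390, 6.7% | 0.781, 11.9% |

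With b = 0 the rate is the nominal 5%, of which 2.5% falls in each direction. The table shows how the test would respond to a shift. It is not evidence that a shift occurs.

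**The case against.** There is a good case that this matters little.

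- **The Visit 1 list may not be a strict running order.** The battery is one bullet defined by its purpose, and staining appears in it and again under the later slit lamp bullet. Several Visit 1 procedures in Table 3, such as contact lens history and autorefraction, are absent from the Visit 1 bullets. Table 3 itself puts the CLDEQ-8 directly after the OSDI. This stands as a reason for caution about what staff would do. It does not remove the point, because section 5.5 defers to 5.4.2 for order, and nothing in 5.4.2 places the CLDEQ-8 ahead of the tests.
- **The questionnaire asks about two weeks of wear, not how the eyes feel now.** This stands. The documents contain no evidence that brief irritation moves such a score. Section 7 calls the discomfort temporary and only possible, and does not tie it to this battery.
- **The consequence is limited.** This also stands. The primary ratings and wear times are collected separately from the CLDEQ-8. Pre-screening with the same questionnaire at home is preferred, though not required, and those answers are not analysed.

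A reader might infer that the order favours DT1 overall. The documents do not support that: lens state differs too and could act in the opposite direction.

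A reader might also see anchoring at Visits 2 and 3, because the home ratings are reviewed before the "In-office subjective ratings of comfort, dryness, vision and handling" are given. In 5.4.2 that sequence is the same for the habitual lens at Visit 2 and for DT1 at Visit 3. Table 3 describes the review as a compliance check. It is not part of this point.

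**Conclusion.** The asymmetry is in the text: the section that governs order lists the habitual-lens CLDEQ-8 after gland expression and staining, and the DT1 CLDEQ-8 before any examination. Carry-over into a two-week recall score is plausible but unproven, and its size is unknown. Taken alone, the order effect could raise only the habitual score, but the net direction of all differences between the visits cannot be determined.

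The effect is confined to the Table 4 CLDEQ-8 comparison and the 12 to 20 entry criterion, where it could move people across either limit. The rejection rates of about 7% to 17% (0.5 point) and 12% to 53% (1 point) rest wholly on assumed shifts and SDs. They should not be read as an estimated false-positive rate for this trial. The point is a minor one, worth acting on because the correction is free.

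**What to change.** In section 5.4.2, Visit 1, move the CLDEQ-8 bullet up to sit with the OSDI, and state that both questionnaires are completed before tear osmolarity and all other ocular tests. This matches Visit 3, where the CLDEQ-8 already precedes examination, and agrees with its place in Table 3. Order the Visit 1 case report form pages the same way.

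The cost is re-ordering one bullet and the form pages. No visit time, procedure or analysis is added. The difference in lens state between the two visits would remain and should be acknowledged when the CLDEQ-8 comparison is reported.

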5.1.3 MASKING

Participants will be masked to the lens type (brand) they will be wearing during the study in order to reduce bias towards or against this product. Lens packages/ blister will be overlabeled.

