5.3 STUDY MATERIALS

5.3.1 LENSES

Details on the lens type used in this study are listed in Table 1.

Table 1: Lens characteristics

Lens	Lens name
Material	Dailies Total1
Manufacturer	Alcon
HC licence #	87774
Dk/t (barrer/cm)	156 (-3.00D)
Sphere power (D)	+6.00D to -10.00D
Base curve (mm)	8.5
Diameter	14.1
Replacement schedule	daily

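### Section 5.4.2 puts DT1 on the eye at Visit 1 before the habitual-lens home ratings and the Visit 2 habitual ratings; take the in-office habitual rating at Visit 1, before any DT1 lens is inserted

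*Combined protocol and SAP*

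**What the plan says.** Section 5.5 states that "The order of procedures is described in sections 5.4.2". In section 5.4.2 the later Visit 1 steps run as follows:

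- The habitual CLDEQ-8 is completed.
- After the slit-lamp examination and refraction, participants "will be fit with DT1 to confirm acceptable visual acuity and lens fit".
- The next item reads "Participants will be asked to insert their habitual lenses to confirm acceptable visual acuity and lens fit".
- Eligible participants go home in their own lenses with a rating form "to be completed at home on Days 1, 3 and 5".

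Visit 2 follows 6-14 days later. Its list includes "In-office subjective ratings of a typical day for comfort, dryness, vision and handling", with total and comfortable wear time over the last month, all for the habitual lens. Later in that visit, "DT1 will be dispensed and the following assessments will be made": acuity, lens surface and fit.

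Three other places put the in-office habitual rating at a different visit. Section 5.1.1 has habitual-lens symptoms assessed at screening and compared with DT1 after a month. Section 5.5.2 gives the typical-day questionnaire at Visits 1 and 3. Table 3 appears to mark the habitual ratings and wear times in the Visit 1 column.

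Section 5.1.3 masks the brand "in order to reduce bias towards or against this product". Section 2 makes end-of-day comfort and dryness, average wear time and comfortable wear time primary.

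**The concern.** The study has one group and a fixed order, habitual lens first and DT1 second, so the habitual value is the only comparator. All four primary endpoints are reported by the participant. Someone with lens-related dryness who has just worn DT1 and then their own lens may score their own lens against that impression over the following days. A good first impression of DT1 would push habitual ratings down, and a poor one would push them up. Over-labelling hides the brand but not how the lens feels. Any such shift passes straight into the paired difference, and the planned tests cannot separate it from a lens effect.

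**Working it through.** **Order of exposure and rating**

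| Habitual measure | Where placed | Relative to DT1 on the eye |
|---|---|---|
| CLDEQ-8 | 5.4.2, Visit 1 | Before |
| Home ratings, Days 1, 3, 5 | 5.4.2 and 5.5.2 | After, on any reading |
| In-office ratings and wear times | 5.4.2, Visit 2 | After |
| The same in-office ratings | 5.1.1, 5.5.2, Table 3: Visit 1 | Not stated |

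Section 11.1 does not say whether home or in-office ratings supply the habitual value in the paired test.

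**The plan's own figure.** Section 5.2.1 uses a two-sided paired t-test, alpha 0.05, power 0.95 and difference/SD 0.60. From the noncentral t distribution, power is 0.9496 at n = 38 and 0.9546 at n = 39, so the stated 39 is reproduced. The implied SD of the paired difference is 5/0.60 = 8.33 points.

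**What a shift would do (illustration; the shifts are assumed).** The standard error is 8.33/√39 = 1.334, and the smallest significant mean difference is 2.024 × 1.334 = 2.70 points. For a systematic shift b, the noncentrality parameter is b/1.334 on 38 degrees of freedom.

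| Shift b (points) | Noncentrality | Share of the 5-point relevant difference | P(significant for DT1), no true difference, shift favours DT1 | P(significant for DT1), true benefit 5 points, shift against DT1 |
|---|---|---|---|---|
| 0 | 0 | 0% | 2.5% | 95.5% |
| 1 | 0.75 | 20% | 10.9% | 83.2% |
| 2 | 1.50 | 40% | 30.9% | 59.1% |
| 3 | 2.25 | 60% | 59.1% | 30.9% |

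The last column uses net differences of 5 − b, that is 5, 4, 3 and 2 points. The documents give no SD for wear time, so the same calculation cannot be made against the 0.5-hour difference in section 11.1.

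**The case against.** The strongest reply is that the mechanism is speculative. The documents describe a check of acuity and fit, give no duration for it and collect no rating of the trial lens. A short chair-side fitting may have little effect on end-of-day comfort or hours of wear a day or more later. Home wear time also rests partly on recorded insertion and removal times, which are less open to suggestion than a 0-100 score. All of this stands. It limits how large the effect can be claimed to be, but it does not change the order of events.

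Three stronger readings are tempting and are not supported:

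- **Every habitual measure follows DT1.** The CLDEQ-8 does not, and three places put the in-office rating at Visit 1, possibly before the fitting.
- **The design favours DT1.** The direction depends on the first impression, which nobody records. The percentages above would follow from any assumed bias of that size and are not evidence that this one exists.
- **The DT1 fitting must move to Visit 2.** Visit 2 does repeat DT1 acuity and fit, and Table 1 lists one base curve and one diameter. But the Visit 1 check decides inclusion criteria 8 and 9, and section 5.4.2 starts the habitual phase only once all criteria are met. Deferring it would leave eligibility open through that phase, and section 8 ties its adverse-event wording to confirmed eligibility.

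It is also true that a fixed order and knowledge of switching lenses would remain after any reordering.

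**Conclusion.** The point holds in a limited form. As section 5.4.2 is written, the habitual home ratings and the Visit 2 habitual ratings and wear times are collected after exposure to the study lens. For the home ratings this is true on any reading; for the in-office ratings it depends on which section is followed. The size and direction of any shift are unknown. The 11%, 31% and 59% figures rest on assumed shifts of 1, 2 and 3 points, n = 39 and SD 8.33, and show only that a small shift would matter in a study powered for 5 points. The sample size is not affected. The change is worth making because an unexposed baseline is available at no cost and the conflict over the rating visit has to be settled anyway.

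**What to change.** 1. Reconcile sections 5.1.1, 5.4.2 and 5.5.2 and Table 3. Collect the in-office habitual rating (comfort, dryness, vision, handling, total and comfortable wear time over the last month) at Visit 1, alongside the CLDEQ-8, and state that it is completed before any DT1 lens is inserted. It should include the end-of-day comfort and dryness items that section 2 makes primary.
2. In section 11.1, name this rating as the habitual value for the paired comparison with the same questionnaire at Visit 3.
3. Describe the habitual home ratings as supportive, because they follow the fitting.
4. Keep the DT1 eligibility fitting at Visit 1, as the last lens step after the habitual-lens check where feasible. Moving it to Visit 2 is optional. The price would be later confirmation of eligibility, and the start of the habitual phase and the adverse-event wording would need matching edits.

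The cost of items 1 to 4 is protocol wording and one table row. No visit, procedure or participant is added. The main comparison then rests on one-month recall for both lenses, with the home ratings as a check on it.

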2 OBJECTIVES

The objectives of the study are:

- To examine and classify DED subtypes in a group of symptomatic CL wearers who are already wearers of daily disposable (DD) CLs (excluding Dailies Total1 (DT1)).
- To assess subjective ratings, cumulative comfort scores, average wear time and comfortable wear time while symptomatic CL wearers use their habitual DD CLs.
- To refit participants with DT1 CLs and assess subjective ratings, cumulative comfort scores, average wear time and comfortable wear time after wearing DT1 for one month.

Primary Endpoint:

- Subjective ratings of end-of-day comfort and dryness (with CLs; 0 to 100 scale)
- Average wear time (hours)
- Comfortable wear time (hours)

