4 HYPOTHESIS

DT1 CLs will provide equivalent or better end-of-day comfort and longer comfortable wear time for DD CL wearers who suffer from DED compared to their habitual lenses.

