5.2.3 INCLUSION AND EXCLUSION CRITERIA

A person is eligible for inclusion in the study if he/she:

1. Is at least 17 years of age and has full legal capacity to volunteer;
2. Has read and signed an information consent letter;
3. Is willing and able to follow instructions and maintain the appointment schedule;
4. As per TFOS DEWS II², have dry eye symptoms (without CL wear) as determined by an OSDI score of ≥ 13 and at least **one** of the following:
 - a. Tear osmolarity $\geq 308\text{mOsm/L}$ or interocular difference $>8\text{ mOsm/L}$
 - b. Non-invasive tear breakup time of < 10 seconds in at least one eye
 - c. More than 5 spots of corneal staining OR > 9 conjunctival spots in at least one eye
5. Reports dryness while wearing DD CLs with CLDEQ-8 score ≥ 12 and $\leq 20^3$
6. Habitually wears soft spherical DD CLs with a power between +6.00D and -10.00D
7. Manifest spectacle cyl $\leq 1.00\text{DC}$ in either eye
8. BCVA $\leq 0.20\text{ log MAR}$ each eye with habitual & DT1
9. Acceptable fit with habitual & DT1
10. Willing to wear DT1 CLs at least 3 days per week and 6 hours per day throughout the study

A person will be excluded from the study if he/she:

1. Is participating in any concurrent clinical or research study;
2. Has any known active* ocular disease and/or infection;
3. Has a systemic condition that in the opinion of the investigator may affect a study outcome variable;
4. Is using any systemic or topical medications that in the opinion of the investigator may affect a study outcome variable;
5. Has known sensitivity to the diagnostic pharmaceuticals to be used in the study;
6. Is pregnant, lactating or planning a pregnancy at the time of enrolment (by self-report);

7. Is aphakic;
8. Has undergone refractive error surgery;
9. Has taken part in another clinical research study within the last 14 days;
10. Current habitual wearer of DT1
11. Any ocular and/or systemic conditions or concomitant medication to contraindicate contact lens wear or be expected to interfere with the primary outcome variables.

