5.5.1 CASE HISTORY

Demographics:

Demographic information from the participant will be obtained, including age, sex and ethnicity.

Medical History:

At screening, information will be obtained from participants about the current medication, allergies, and any medical conditions. At visits 2 and 3 participants will be asked about changes in their medication or health.

Contact Lens History:

Information will be obtained from the participant about the current contact lens type (lens name, brand), lens power, lens wear days and use of artificial tears. Participants will be asked how many years of lens wear experience they have and how long they have been wearing DD lenses.

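### Only the DT1 period carries a minimum wear instruction, so where habitual wear is below 6 hours the instruction itself can raise DT1 average wear time, a primary endpoint

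*Combined protocol and SAP*

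**What the plan says.** Section 5.4.2, Visit 1: once eligible, "the participant will be instructed to wear their habitual DD CLs as usual until their next scheduled visit". Lenses must be worn on the rating days, but no number of hours is set. Section 5.5.2 fixes those days: "This questionnaire will be completed at home on Days 1, 3, 5 after visit 1".

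Section 5.4.2, Visit 2: participants take home a month of DT1 and are "instructed to wear the lenses at least 3 days per week and 6 hours per day throughout the study".

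Section 5.2.3, inclusion item 10, names DT1 alone: "Willing to wear DT1 CLs at least 3 days per week and 6 hours per day throughout the study". Item 6 covers habitual lens type and power, not hours. Section 5.5.1 records "current contact lens type (lens name, brand), lens power, lens wear days and use of artificial tears", again without hours. Total wear time with habitual lenses is nevertheless collected: in the home diary, and in an office rating over the last month. Section 5.4.2 places that rating at Visit 2, while Table 3 and section 5.5.2 place it at Visit 1.

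Section 2 lists average and comfortable wear time among the primary endpoints. Section 11.1 plans equivalence and superiority evaluations for the primary outcomes, with 0.5 h as the relevant difference for both wear times. The hypothesis in section 4 names only "longer comfortable wear time for DD CL wearers who suffer from DED compared to their habitual lenses".

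**The concern.** The instruction puts a floor under the measured outcome in one condition only. The order is fixed (habitual first, DT1 second) and there is no randomization or parallel group, so the design cannot separate an effect of being told to wear lenses for 6 hours from an effect of the lens. Compliance with wear is reviewed at Visits 2 and 3 (Table 3), and section 9 provides for discontinuing people who do not follow procedures, so the floor may be enforced. Section 11.1 contains nothing to offset it.

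Any effect moves the average wear time difference towards DT1. That helps a superiority claim and can defeat an equivalence claim. Participants are selected for dryness with lenses, so short habitual wear is plausible, but the documents do not show it.

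**Working it through.** **The plan's own figure.** Section 5.2.1 gives n = 39 for a two-sided paired t-test with alpha 0.05, power 0.95 and diff/SD 0.60. The normal approximation, ((1.960 + 1.645)/0.60)², rounds up to 37. The noncentral t gives power 0.9496 at n = 38 and 0.9546 at n = 39, so 39 reproduces. It was set for the subjective ratings and says nothing about wear time.

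**Inputs.** From the documents: a 6 h floor for DT1, none for habitual lenses; 39 completers; relevant difference 0.5 h; 3 habitual and 6 DT1 diary days. Assumed: daily wear X is Normal(m, s) with m = 8, 10 or 12 h and s = 2 or 3 h; full compliance; no lens effect.

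**Mean artefact.** If every day below 6 h is raised to 6 h, the shift is

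A(m, s) = E[max(6 − X, 0)] = (6 − m)·Φ((6 − m)/s) + s·φ((6 − m)/s).

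| Habitual mean | Share of days below 6 h (s = 2; s = 3) | Artefact (s = 2; s = 3) |
|---|---|---|
| 8 h | 15.9%; 25.2% | 0.167 h; 0.453 h |
| 10 h | 2.3%; 9.1% | 0.017 h; 0.127 h |
| 12 h | 0.1%; 2.3% | 0.001 h; 0.025 h |

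Half compliance halves these values. As a distribution-free guide, the shift is the share below 6 h times the mean shortfall: 10% × 1 h = 0.10 h, 20% × 1.5 h = 0.30 h, 25% × 2 h = 0.50 h.

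**Effect on the test.** Simulation of the diary comparison with n = 39, 20,000 trials and no lens effect. Between- and within-person SDs are 2.5 and 1.66 h for s = 3, and the same ratio (1.67 and 1.11 h) for s = 2. The table gives the chance of a two-sided 5% paired t-test favouring DT1; the nominal value is 2.5%.

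| Habitual mean | s = 2 | s = 3 |
|---|---|---|
| 8 h | 22% | 52% |
| 10 h | 3% | 9% |
| 12 h | about 2.5% | 3% |

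For s = 3, the chance of showing equivalence within 0.5 h (two one-sided 5% tests, an assumed method) falls from 67% without the floor to about 9% at 8 h and 54% at 10 h, and is unchanged at 12 h.

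**Matched minimum.** With the floor in both periods the simulated mean difference is 0.00 h at every mean. The price is attenuation. A true gain of 0.5 h is seen as 0.5 − [A(m) − A(m + 0.5)]:

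- m = 8, s = 3: 0.5 − (0.453 − 0.340) = 0.39 h; s = 2: 0.5 − (0.167 − 0.101) = 0.43 h.
- m = 10, s = 3: 0.5 − (0.127 − 0.088) = 0.46 h; s = 2: 0.49 h.

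**Excluding short wearers.** Suppose the DT1 minimum is dropped but the analysis keeps only people whose habitual diary mean is at least 6 h. Regression to the mean then gives −0.135 h at m = 8 and −0.048 h at m = 10 (s = 3), a bias against DT1.

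**The case against.** The strongest reply is that no effect is shown. Without a habitual wear distribution, every figure above is conditional, and at means of 10 h or more with s = 2 there is almost nothing to see. Item 10 may also deter some of the shortest wearers. This stands, and it limits the point to an inexpensive improvement.

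The test probabilities assume diary data, but the plan does not name the source. Table 4 ties the home ratings only to the DT1 time course, and office ratings of wear time over the last month exist for both lenses. This stands too. The mean artefact does not need the diary's day counts; the percentages do. The equivalence figures are especially fragile: adding person-by-lens variation with an SD of 1 h lowers the chance of equivalence to about 28% at a mean of 12 h, where the floor hardly acts.

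A reader might infer that habitual hours go unrecorded because the lens history omits them. They do not: the diary and the office rating both capture them.

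A reader might take the wording about the whole study in item 10 and at Visit 2 to cover the habitual period. It does not. Item 10 names DT1, and the instruction is given when DT1 is dispensed.

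A reader might also treat comfortable wear time as immune and so as a full check. The minimum does not act directly on time to discomfort, but the plan does not say how that time is scored when lenses come out before discomfort starts. If removal time is used, the minimum could raise it as well. It is a partial check only.

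**Conclusion.** The asymmetry is explicit, bears on a primary endpoint and is not offset anywhere in the analysis plan. Its direction is known: average wear time moves towards DT1. Its size is not. Under the stated assumptions it runs from about zero to 0.45 h, with false significant results for DT1in about 22 to 52% of trials at a habitual mean of 8 h, 3 to 9% at 10 h and about 3% at 12 h.

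The documents do not support the stronger reading that a DT1 advantage in average wear time would be an artefact, or that the artefact reaches the 0.5 h threshold. No case in the table does. Reaching it would take, for example, a quarter of wearers falling short by 2 h on average. The point is worth acting on because the change is small and the team cannot know in advance which case applies. Confidence is medium.

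**What to change.** Choose one of two wording changes.

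1. At Visit 1, give the same instruction for habitual lenses: at least 3 days per week and 6 hours per day. The cost is less natural habitual wear and the attenuation shown above. This works fully only if the habitual value comes from days after the instruction, such as the Days 1, 3 and 5 diary. A rating over the last month taken at Visit 2 would include only the 6 to 14 days since Visit 1.
2. Drop the 6-hour minimum for DT1 from the Visit 2 text and item 10. The cost is less assured DT1 exposure.

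In either case, state in section 11.1 which source supplies average wear time, report the share with habitual wear below 6 h from the wear times already collected, and read average wear time alongside comfortable wear time. Do not exclude people on that noisy baseline.

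No new entry rule or history item is needed. Once the instructions match, an entry rule removes no further bias. It could exclude about 23% of otherwise eligible people at a mean of 8 h (s = 3, error SD of the entry answer 1 h). Against the screening limit of 60 in section 5.2.2, that leaves 60 × 0.77 ≈ 46 before any other screen failure, with about 43 to be dispensed.
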